4.1. Study Design

4.1.1. Describe experimental design of the study. Include sequential and/or parallel phases of the study, including durations, and explain which interventions are standard of care.

This feasibility study assesses feasibility in six domains and provides preliminary evidence of treatment response, through a pilot randomized controlled trial (RCT). The pilot RCT compares the intervention group (BA plus as Treatment as usual) with the control group (Treatment as usual). We will enroll 40 subjects (20 in each

group), conduct a baseline interview, randomize into the two groups, and then conduct a follow-up interview 3 months later. Subsequently, a qualitative phone interview to assess the experience of the intervention along with satisfaction/acceptability will be conducted with those in the intervention group. The BA intervention will be delivered in 6 sessions over 3 months by OTs trained in BA for post-TBI depression.

Procedure. At the baseline interview, the interviewer will review the study, answer veterans' questions, obtain Informed Consent, screen for depression using the CES-D scale and item 9 of the PHQ-9, and conduct the baseline interview battery. If the participant does not meet inclusion criteria based on the CES-D, and PHQ-9 at this time, they will not be included in the study as a randomized participant. We will thank them for their time, and they will receive compensation for the visit. They will also be offered referrals for services as appropriate.

Response cards presenting each question's response format will be employed to reduce response burden and facilitate interview progress. In previous studies, response cards were found helpful and acceptabl.^{47,48} The estimated time of the baseline interview is 1.3 hours, including time for Informed Consent. Interviews of this length have been conducted with veterans with TBI and depression in previous research and were not found excessively burdensome.^{47,48} The interview will be conducted in the setting preferred by the participant, a rehabilitation clinic office or his/her home. In our experience, most who complete the Baseline interview will be willing to continue to participate. Veterans who do not wish to continue with the study after the baseline interview will not be randomized or count towards our accrual goals.

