Within 48 hours of the baseline interview, eligible veterans will be randomized using the method of random permuted blocks (to control for possible changes over time in subject mix) and concealed allocation. Those randomized to BA will be contacted within 5 days by the interventionist and scheduled for the first session.

Those randomized to BA will receive the 6-session BA intervention (as well as treatment as usual [TAU]). Control participants will receive TAU only (which may include current medical and mental health treatments.) Three months after Baseline, a blinded interviewer will conduct the follow-up interview in

person or on the phone with all veterans. Subjects will be sent reminder letters two weeks prior to this 3-month follow-up interview.

Study instruments and when they are used are described in a table in Section 8 and included in the Appendices.

Study staff will offer to share findings with participants.

4.1.2. Include a description of how anticipated risk will be minimized and include an analysis of risk vs. potential benefit.

This study is designed for persons with TBI who have a CES-D score of 16 or greater at both screening and baseline. Such a score indicates the presence of clinically significant depressive symptoms. Those who answer affirmatively (1, 2, or 3) at the baseline interview to item 9 from the PHQ-9, indicating suicide ideation, will not be eligible for the study.

Because this study involves interviews with persons with TBI who have at least mild depression, there is a minimal risk that the interviews may contribute to emotional discomfort in the discussion of personal matters. In our previous study of veterans with TBI in their homes (the large majority of whom scored above the cutoff for clinical depression on the CES-D Short Form), using many of the same interview instruments as proposed, we encountered no upset or excessive fatigue with any participants nor did any adverse events occur as a result of study participation.

The study poses minimal risk to study participants, based on experience with our earlier in-home intervention study with veterans with TBI, the literature on rehabilitation interventions with persons with TBI, and literature on BA. The risk of burden or fatigue from the interview or intervention is also low.

Risks to privacy or subject discomfort about disclosing or considering sensitive information

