The proposed study may provide benefits to study participants. Participants may acquire skills to help reduce their depressive symptoms and increase their participation in activities and the community. Participation may lead to more veterans with TBI being assessed and identified as having mild or moderate depressive symptoms. It is also possible that participants may have no direct benefit.

The present application of BA to TBI-related depression is designed to augment current clinical care for TBI. It does not take the place of other treatments for depression that persons with TBI may be receiving. Study participants are not asked to stop other treatments they are receiving for TBI or mental health problems. Results from the study will allow us to assess the feasibility of BA for veterans with post-TBI depression and will provide preliminary data to support a future larger efficacy trial. This feasibility study and future research may generate new knowledge around the development and evaluation of interventions that reduce depression and improve community reintegration for veterans with TBI.

Risk vs. Benefits

Knowledge gained through this feasibility study and future larger studies has the potential to advance the care of persons with depression post TBI and to extend our knowledge on the feasibility and efficacy of interventions for this population. Given that TBI is a major public health problem for military and civilian populations and in light of the high prevalence of depression post-TBI, the potential benefits for this population and society outweigh the potential risks

4.1.3. Provide description of the study population (delineate all categories of subjects – patients, providers, family members, employees, etc.). Include anticipated enrollment numbers.

A total of at least forty male and female Veterans at a VA outpatient Rehabilitation Medicine Service will be recruited to participate. We will oversample women to assure approximately 10% in each arm.

4.1.4. As applicable, provide information on any added protections for vulnerable populations.

N/A

4.1.5. If applicable include information on data and specimen banking.

N/A

5. Recruitment Methods

5.1. State how many subjects will be needed.

At least, forty male and female veterans at a VA outpatient Rehabilitation Medicine service will be recruited to participate.

5.2. **Describe when, where, how and by whom potential subjects will be identified and recruited.**

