Quality of Life in TBI	The QoL-TBI ^{63, 64, 65, 66} is a 37-item patient-centered measure that captures the individual's perception of his/her health-related quality-of-life (HRQoL) in cognition, self-care, daily life and autonomy, social relationships, emotions, and physical problems. Baseline & Follow-up interviews.
Demographics & military characteristics	These characteristics are age, sex, years of education, race, Hispanic ethnicity, marital status, employment status, financial difficulty, combat exposure, and war cohort. Baseline interview.
Relevant health data	Years since most recent TBI, severity of TBI, co-morbidities, source of injury (e.g., blast exposure, vehicular, fall), number of TBIs, and history of prior TBIs and of depression. Baseline interview and PCRS review.
Post-Traumatic Stress Disorder	The 20-item PCL-5 ^{67, 68} is a self-report measure of PTSD symptom severity assessing 20 symptoms experienced in the past month that correspond to the DSM-V. Each item is rated on a 5-point Likert scale, from 1 (not at all bothered) to 5 (extremely bothered). A score between 31-33 indicates probable PTSD. ⁸⁶ Baseline interview.
Patient self-ratings of functioning	Self-rated competency in daily activities is measured using the Patient Competency Rating Scale (PCRS), ^{69,70} a 30-item standardized measure of patient competency designed for TBI populations. The stem question is, "How much of a problem have you had (in the past month) in ...?" The response format is a five-point Likert scale from 1 (cannot do) to 5 (can do with ease). Higher scores indicate better functioning. Baseline and Follow-up interviews.
Healthcare services utilization	Veterans with TBI may use outpatient and inpatient care, mental health services, social services, and military service-connected and/or disability services. This Checklist will assess frequency of use of 11 healthcare services in the past month and since the baseline. Baseline and Follow-up interviews.
Behavioral Activation	The 23-item Behavioral Activation for Depression Scale (BADS) ⁷¹ measures engagement in social and occupational activities hypothesized to underlie depression and targeted for change by BA, using 7-point Likert responses from 0 (not at all) to 6 (completely). Baseline and Follow-up interviews.

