- (e) Participant comprehension: Interviewer and interventionist will note areas of participant difficulty understanding interview questions and intervention activities. Missing data will also reflect difficulty.
- (f) Research burden: Length of time to complete interviews will be recorded using start and stop time data on the interview. The interviewer will record participant fatigue, wish to take breaks, and/or emotional distress.

Aim 2 will assess change in participant response by comparing Group 1 (BA + TAU) and Group 2 (TAU) on outcomes at T2 (3-month follow-up). We will first conduct

descriptive analyses separately for the BA and control groups to characterize the sample and assess the success of randomization in balancing the two groups. We will inspect trends, directions of change in the two groups, and associations between baseline characteristics (T1) and CES-D scores at follow-up (T2). The same trends and changes will be inspected for the secondary outcomes of CR and QOL. Analyses will be conducted using SPSS version 25.

Aim 3 is to develop and refine the BA protocol, manual, and interview measures. In the first 3 months, an expert panel comprising the investigators, interventionists, interviewer, clinic staff, and two veterans with TBI will review and modify the existing protocol and manual to adapt them for hallmark deficits of TBI. The panel will meet monthly to monitor the study, assessing need for additional compensatory strategies and removal or alteration of strategies that depend on: abstract thinking; patients' understanding of TBI-related depression; awareness of emotion and its regulation; and interpersonal issues. Interview measures will be assessed for participant comprehension, sensitivity, and burden. This pilot study will produce a refined BA protocol and manual for post-TBI depression whose efficacy will be evaluated in a larger RCT.

An Exploratory Aim will examine engagement in activity as the mechanism underlying effects of BA. Although mediation analysis is beyond the scope of this feasibility study, we will explore characteristics of activity engagement using the BADS and its associations with the BA intervention and with depression.

10. Withdrawal of Subjects

10.1. Describe any anticipated circumstances under which subjects will be withdrawn from the research without their consent.

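### Oversampling women cannot assure about 10% in each arm when the allocation described has no sex stratum: with 4 women among 40, one arm has none 10.6% of the time (the BA arm 5.3%)

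*Combined protocol and SAP*

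**What the plan says.** Section 4.1.3 makes a statement about each arm: "We will oversample women to assure approximately 10% in each arm". The same item gives the total: "A total of at least forty male and female Veterans at a VA outpatient Rehabilitation Medicine Service will be recruited to participate". Section 4.1.1 sets the allocation at "We will enroll 40 subjects (20 in each" group), and says that veterans who stop after the baseline interview "will not be randomized or count towards our accrual goals".

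Section 4.1.1 also gives the allocation method. Eligible veterans are "randomized using the method of random permuted blocks (to control for possible changes over time in subject mix) and concealed allocation". It states neither a block size nor a stratification factor. The recruitment text in Section 5.2 describes no separate procedure for women.

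Sex is recorded at the baseline interview, before randomisation (Section 8.1, Table 2: "These characteristics are age, sex, years of education, race, Hispanic ethnicity"). In Section 9.2, the Aim 2 analysis begins with descriptive summaries by group, used to "assess the success of randomization in balancing the two groups".

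**The concern.** The share of women in the trial and their division between arms are controlled at different steps. Recruitment governs the first and allocation governs the second. The plan promises a result for the second but describes an action only on the first. Permuted blocks balance the arms over calendar time, which is the purpose the plan gives for them. They do not balance a characteristic unless the lists are kept separately by that characteristic. The Aim 2 balance check comes after allocation, so it can reveal an imbalance but not prevent one.

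What is at stake is limited. The interventionist's acceptance rating, the participant satisfaction scale, session attendance and the final interview on the experience of BA come from BA participants only. If no woman is allocated to BA, the study yields none of these for women, although it set out to oversample them. Staff acceptability, eligibility, willingness to enter the study and interview burden do not depend on the BA arm. The effect on the descriptive Aim 2 comparison is minor.

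**Working it through.** The plan gives no calculation behind the 10%, so there is no figure to reproduce. The check asks how often the described allocation delivers the stated share.

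**Inputs**
- 40 randomised, 20 per arm (Section 4.1.1).
- 10% women per arm (Section 4.1.3): 0.10 × 20 = 2 per arm, or 4 of 40. The count of 4 is an assumption, since the plan fixes no number.
- No stratification by sex, and women entering in random order (also an assumption).

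**Split of 4 women, unstratified.** The number k allocated to BA is hypergeometric: P(k) = C(20,k) × C(20,4−k) / C(40,4), with C(40,4) = 91,390.
- No women in BA: C(20,4)/C(40,4) = 4,845/91,390 = 5.3%.
- No women in one arm or the other: 2 × 5.3% = 10.6%.
- 2:2, exactly 10% in each arm: 190²/91,390 = 36,100/91,390 = 39.5%.
- 3:1 in either direction (15% against 5%): 2 × 1,140 × 20/91,390 = 49.9%.
- At least one woman in each arm: 100% − 10.6% = 89.4%.

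**Dependence on the number of women.** P(BA has none) = C(20,k)/C(40,k) for k women, and double that for either arm.

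| Women | BA has none | One arm has none |
|---|---|---|
| 3 | 1,140/9,880 = 11.5% | 23.1% |
| 4 | 4,845/91,390 = 5.3% | 10.6% |
| 5 | 15,504/658,008 = 2.4% | 4.7% |
| 6 | 38,760/3,838,380 = 1.0% | 2.0% |

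Both arms have at least 2 women 39.5% of the time with 4 women, 65.8% with 5, 81.8% with 6 and 95.6% with 8. Eight women would be 20% of 40, twice the stated share.

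**Dependence on block size, entry order and total.** Simulated unstratified blocks of 2 to 40 gave 10.4% to 10.8% for one arm without women when entry order is random. If order is not random, the figure runs from 0% (four women filling one block of 4) to 2 × (1/2)⁴ = 12.5% (each woman in a different, independent block). With 4 women in a total of 42 to 60, it is 10.7% to 11.2%.

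**Separate list for women, 4 women**
- Block size 4: always 2:2.
- Equal mix of 2 and 4: P(2:2) = 1/2 + 1/4 + (1/4)(2/3) = 91.7%, otherwise 3:1.
- Block size 6: P(2:2) = C(4,2) × C(2,1)/C(6,3) = 12/20 = 60%.

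With block size 4, or the mix of 2 and 4, neither arm is without women for any count of 3 or more.

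**The case against.** The sentence sits in the item on population and enrolment, not in the randomisation text, and can be read as a recruitment intention: with 1:1 allocation, 10% women overall gives an expected 10% in each arm. The plan sets no tolerance for the word approximately. If 3:1 is accepted, the design as described meets the target 89.4% of the time. That is a fair account of how often things would turn out acceptably, but an expectation is not an assurance, and the sentence promises the latter.

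The harm that matters is a BA arm without women, so 5.3% is the figure tied to it rather than 10.6%. This stands. It also stands that 4 women is an assumption and that the risk falls to 2.0% (BA 1.0%) with 6.

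No planned output depends on the split. Section 2.2 states no hypotheses, the Aim 1 criteria are not broken down by sex, and Aim 2 is descriptive. Even a perfect 2:2 split gives BA data from two women, too few to estimate a rate. This keeps the point at low severity but does not make the sentence true.

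Stratification also does not recruit women. It divides whoever enters, and Section 5.2 does not say how oversampling will be done. With only 2 women and block size 4, both go to the same arm one time in three. This stands as a limit on the remedy.

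Finally, the public document is an excerpt, and lists stratified by sex may exist without being mentioned. If so, one sentence settles the matter.

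**Conclusion.** The concern holds, at low severity. Section 4.1.3 claims a per-arm property that neither oversampling nor the allocation described in Section 4.1.1 provides. With 4 women among 40, split 20:20 without stratification and entering in random order, the BA arm has no women 5.3% of the time, one arm or the other has none 10.6% of the time, and the exact target is met 39.5% of the time. The size depends on the assumed number of women. The lack of a mechanism does not. The conclusion rests on the public text, in which no stratum by sex is named.

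**What to change.** State the mechanism in one sentence in Section 4.1.1: separate concealed permuted-block lists for men and women, with block size 4, or a concealed mix of 2 and 4, in the women's list. Sex is already available before randomisation. If the lists are already stratified by sex, say so there. If randomisation is under way without stratification, reword Section 4.1.3 so that the 10% refers to the whole randomised sample, and report the number of women in each arm.

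The cost is one extra list or one reworded sentence. Stratifying has two drawbacks. Assignments in a small stratum are easier to predict if the block size is guessed; with blocks of 2, every second one is determined. Incomplete blocks can also disturb 20:20. With blocks of 4 in both lists:
- 4 women and 36 men give exactly 20:20.
- 5 women and 35 men leave an odd participant in each list, so the result is 20:20 half the time and 21:19 otherwise.
- 6 women and 34 men leave two places used in each list's last block (difference 0 with probability 2/3, +2 or −2 with probability 1/6 each). P(20:20) = (2/3)² + 2 × (1/6)² = 50%, P(within 21:19) = 1 − 2 × (1/6)² = 94.4%, and the split never exceeds 22:18.

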A Feasibility Study of Behavioral Activation in the Rehabilitation of Veterans with Post-TBI Depression

PI: [name], RN, FAAN
NCT04976621

Human Participant Information and Protocol Summary Excerpted from IRB approved Form 101, V. 6.0, Jan. 18, 2023, Approved by CMCVAMC IRB on 3/6/2023

Section 5: Human Participant Information

NOTE: A participant is considered "enrolled" at the time the consent is signed so this number should include an allowance for screen failures prior to randomization.

1. **How many participant records will be reviewed PRIOR to enrollment/consent occurring?**
We may review up to 300 records and send up to 300 letters in order to obtain a sample of 40 subjects.
2. **How many participants will be screened PRIOR to enrollment/consent occurring?**
We may conduct Phone Screens on up to 300 potential subjects (however it is most likely that we will screen about 70).
3. **How many participants will be enrolled (total number to include randomized and screen failures AFTER consent is obtained)?**
60
3.1. Will all research activity be the same at all sites? Yes No N/A
3.2. If no, please describe the activity that is different or limited (For example; 2 sites will analyze data only, or, 1 site will consent and enroll all participants etc.):
4. Are there any further screening procedures after enrollment? Yes No
4.1. If yes, describe: Screening for the inclusion criteria on the CES-D and PHQ item 9 and exclusion criteria for the person with TBI (presence of psychosis, presence of aphasia, PHQ-9 affirmative response on item 9 indicating suicide ideation, or indication of dementia based on difficulty responding to interview questions will occur after consenting.
5. **Are non-Veterans being enrolled?** **NOTE:** This does not include non-Veterans enrolled at non-VA sites. Yes No
5.1. If yes, provide justification.

NOTE:

- Every non-Veteran should sign VA form 10-0483, Acknowledgement of the Notice of Privacy Practices (ANOP)
- Once the ANOP is signed, the research study staff must send the non-Veteran's name to the CMCVAMC Privacy Officer via encrypted e-mail. The signed ANOP must be kept in the research study binder.
- If an oral informed consent is used, the NOP should be sent to the non-Veteran via postal mail. In addition, the research study staff must write a Note-to-File that the NOP was sent to the non-Veteran.

6. **Does this project target a specific race, gender or ethnic group as participants?**
Yes No

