Names of veterans meeting inclusion criteria for age, diagnosis of TBI, and severity of TBI will be given by the Polytrauma Team, and then we will mail these Veterans I a letter of invitation that introduces the study and invites them to call the study phone number to express interest in the study. The letter also informs them that a member of the research team will be calling them to discuss the study. When a veteran expresses interest in continuing the discussion about the study, the team members will provide more information, answer questions, and determine eligibility. Once an individual is deemed likely eligible, the research interviewer will schedule the baseline interview.

A study flyer with a study phone number will be posted at the CMCVAMC, and Veterans may contact us from that.

5.3. **Describe materials that will be used to recruit subjects, e.g., advertisements.**

Include materials as an appendix or separate attachment

Informational flyer (Appendix 4); Letter of Invitation (Appendix 5); Telephone script used after letter (Appendix 2)

5.4. **Describe any payments to subjects, including the amount, timing (at the end of the study or pro-rated for partial study participation), method (e.g., cash, check, gift card), and whether subjects will experience a delay in receiving the payment.**

There will be incremental payment for interviews: \$40 for completion of the Baseline (BL) interview and \$50 for the follow-up interview at 3 months.

6. **Informed Consent Procedures**

6.1. **Indicate if informed consent will be obtained and/or if you are requesting a waiver of informed consent or waiver of documentation of informed consent. If the research involves multiple phases, specify for which phases of the research the waiver(s) is being requested and/or the informed consent will be sought.**

We will obtain informed consent at the Baseline (BL) visit. We will obtain a Waiver of HIPAA for prescreening (letters, post-letter phone call.)

6.2. **Describe who will be obtaining informed consent, if applicable, and any circumstances that may need to be addressed (e.g. subjects with impaired decision making ability and the use of a legally authorized representative, etc.)**

The interviewers will obtain informed consent at the BL visit. This will take place at the CMCVAMC or at the subject's home, whichever the subject prefers. Subjects with impaired decision making ability or requiring a legally authorized representative will not be included.

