Acceptability to veterans and staff, assessed using qualitative and quantitative measures. Qualitative: This analysis will be conducted for open-ended interview questions concerning the experience of receiving BA (for veterans) and the process of its implementation in the rehabilitation setting (for clinic staff). After verification of transcript accuracy for interviews, ATLAS.ti will be used to facilitate data organization, coding, and retrieval. Qualitative content analysis⁷⁴ will inductively generate codes and categories. Line by line coding will be conducted to identify codes or statements of meaning (level I coding) that are then grouped into larger categories (level II, coding for themes). Strategies to support scientific rigor will be followed: for credibility (member checking findings with a subsample of participants); dependability (audit trial); transferability (thick description); and confirmability (audit trial).⁷⁵

Quantitative: (1) On the Acceptance/Receipt Scale completed by the interventionist (final Delivery Assessment form), at least 75% should score ≥ 3.0 (Appendix 7); (2) On the Satisfaction Scale, administered to BA participants during the final interview (Appendix 9), $\geq 75\%$ should score ≥ 3.0 . (3) Willingness to participate in future related studies should be $\geq 75\%$. Criteria are based on our past study.⁴⁷

- (a) Process: (1) For recruitment, $\geq 50\%$, percent of veterans will be eligible to participate, and $\geq 30\%$ will be willing to participate. (2) For retention, $\geq 75\%$ of veterans in BA will attend ≥ 4 sessions, and $\geq 75\%$ will complete the study. (3) Less than 15% deviation from protocol on the Treatment Fidelity Checklist will occur.
- (b) Practicality: Resources of the rehabilitation setting that support the BA intervention and constraints that may interfere will assess the probability that BA can be implemented. Resources and constraints will be assessed by interventionists, the project manager, and clinic staff through discussions on issues including scheduling, coordination with other appointments, staff time, and space providing privacy.
- (c) Treatment safety: Number of adverse events (study-related and unrelated) will be monitored.
- (d) Eligibility criteria: The team will assess whether these criteria were too broad or restrictive.

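### Does the recruitment criterion of at least 30% willing need a stated numerator and denominator before it can be used?

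*Combined protocol and SAP*

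**What the plan says.** Section 9.2, Aim 1 (a) Process, gives the recruitment criterion in one sentence: at least 50% "percent of veterans will be eligible to participate", "and $\geq 30\%$ will be willing to participate". The session-attendance criterion that follows it does name its base, the veterans in the BA arm. Section 2.1 (Aim 1, Process) and Section 9.1 list recruitment, refusal and retention rates as things to be assessed, without defining them.

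The path to randomisation has several stages:

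- **Invitation.** Section 5.2 of the Protocol Summary has letters mailed to veterans already filtered on age, TBI diagnosis and severity. A flyer is a second route without a letter.
- **Phone contact.** "Once an individual is deemed likely eligible, the research interviewer will schedule the baseline interview".
- **Consent and baseline.** Consent is taken at the baseline visit (Section 6.1). Further checks follow consent: "Screening for the inclusion criteria on the CES-D and PHQ item 9 and exclusion criteria for the person with TBI" (Human Participant Information, item 4.1).
- **After baseline.** "Veterans who do not wish to continue with the study after the baseline interview will not be randomized or count towards our accrual goals" (Section 4.1.1).

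The planned volumes are in Human Participant Information, items 1 to 3: "We may review up to 300 records and send up to 300 letters in order to obtain a sample of 40 subjects"; "We may conduct Phone Screens on up to 300 potential subjects (however it is most likely that we will screen about 70"; and 60 enrolled, where enrolment means signed consent and the total includes screen failures after consent. Section 4.1.1 gives 40 subjects, 20 per group.

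**The concern.** Eligibility is judged at least twice, by phone and again after consent. Willingness is shown at three points: interest after the letter, consent at the baseline visit, and agreement to go on after the baseline interview. A percentage without a base can be computed at any of these stages, and a veteran who consents and then declines randomisation could be counted as willing or not.

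Section 2.2 states no hypotheses, and Aim 2 is an inspection of trends. The Aim 1 thresholds are therefore the plan's main numerical standards. If one set of recruitment counts could be declared above or below 30% after it has been seen, the criterion would say little to those planning the larger trial.

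**Working it through.** **Inputs.** Randomised: 40 (Section 4.1.1). Consented: 60, including an allowance for screen failures (Human Participant Information, item 3). Phone screens: about 70 forecast, 300 at most (item 2). Letters: 300 at most, no forecast (item 1). Thresholds: 50% and 30% (Section 9.2). The plan states no willingness rate of its own, so there is no figure to reproduce.

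**Formulas.** Rate = numerator / base. Largest base that still passes = numerator / 0.30, rounded down to a whole number.

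| Base | 40 randomised | 60 consented |
|---|---|---|
| 70 phone-screened (forecast) | 40/70 = 57.1%, pass | 60/70 = 85.7%, pass |
| 300 phone-screened (ceiling) | 40/300 = 13.3%, fail | 60/300 = 20.0%, fail |
| 300 letters (ceiling) | 40/300 = 13.3%, fail | 60/300 = 20.0%, fail |
| 150 eligible (50% of 300) | 40/150 = 26.7%, fail | 60/150 = 40.0%, pass |

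**Where the letter base turns.** With 40: 40/0.30 = 133.3, so 40/133 = 30.1% passes and 40/134 = 29.9% fails. With 60: 60/0.30 = 200, so 60/200 = 30.0% passes and 60/201 = 29.9% fails. This assumes that every participant came through a letter; flyer contacts would have to be counted apart.

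**Like for like.** The contrast between screened and invited is partly one between a forecast and a ceiling. At 300 the two bases give the same 13% to 20%. Passing among those screened holds at the forecast of 70, not at every permitted volume.

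**The eligibility rate.** It is open in the same way. If 40 are randomised from 70 screened, at least 40/70 = 57% were eligible, above 50%. From 300 screened, 40 randomised guarantees only 40/300 = 13%, so the 50% is no longer assured.

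**Do the thresholds conflict with the volumes?** Reading the 30% as willing among eligible, 300 × 0.50 × 0.30 = 45, which covers 40. That reading fits the ceiling, though the plan does not state it. It does not carry over to 70 screens, where 70 × 0.50 = 35 eligible is already below 40. The ceiling and the thresholds are compatible, and the thresholds are floors for judging recruitment, so nothing here is a contradiction.

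**What would fixing a base gain?** Suppose the base were veterans found eligible by phone and the numerator those who consent. With 70 screened, at most 70 are eligible, so the rate is at least 40/70 = 57% whenever 40 are randomised. At the forecast that version cannot fail once accrual is met. The letter base could fail, but at a point set by how many letters are sent, which the plan does not forecast.

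**The case for a change.** The best case for a change is that a threshold set in advance should not leave its base to be chosen afterwards. The pass or fail result does move with the base, and among 150 eligible the numerator alone moves it (26.7% against 40.0%). The remedy would be a sentence or two in Section 9.2, with thresholds and procedures unchanged, and the thresholds carry weight in a study without hypotheses.

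Much of this stands: the bases are missing, no other section supplies them, and the arithmetic is right. Three things limit its force. First, Section 9.2 ties no decision to proceed, stop or redesign to the 30%. Second, Sections 2.1 and 9.1 already make recruitment and refusal rates a subject of assessment, and once the stage counts are shown a reader can compute any version. Third, the numerators are less free than they seem: the form defines enrolment as signed consent, and Section 4.1.1 excludes from accrual those who stop after baseline. Neither defines willing, but both narrow how such a veteran would be classified.

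One uncertainty remains. The plan mentions screening forms, a tracking master list and tracking files (Section 4.1.2) but does not say that they hold counts before consent.

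**Conclusion.** No change to the plan follows. The two recruitment rates lack stated bases, and the result against 30% can depend on the one used: 57% to 86% at the forecast of about 70 phone screens, 13% to 20% at 300 screens or 300 letters, with the letter base turning at 133 letters (40 randomised) or 200 (60 consented). These ranges assume 40 randomised to 60 consented and, for letters, that all participants came by letter. They are not predictions.

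This is missing detail rather than an error. The stated thresholds and volumes do not contradict each other, nothing is decided on the 30%, and writing down one base would either test little at the forecast or depend on a number of letters not yet known. The usual report, with counts from letters to randomisation, flyer contacts and post-baseline decliners shown separately, and each percentage given with its base, fills the gap. This conclusion assumes that the team keeps those counts, as assessing refusal rates requires.
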